## **5.3.** CONCOMITANT MEDICATIONS

All concomitant treatment should be verified and reported in the electronic Case Report Form (eCRF) at each visit.

#### 5.3.1. Prohibited treatments

VMAT2 inhibitors such as tetrabenazine, deutetrabenazine, or valbenazine are forbidden within  $\underline{3}$  months prior to randomization and at any time during the whole study.

Neuroleptics indicated to treat chorea such as haloperidol, pimozide, or tiapride, and all other neuroleptics used off label as dopamine D2 receptor blockers to treat chorea are forbidden within  $\underline{2}$  months prior to randomization and at any time during the whole study.

The following treatments are forbidden within 1 month prior to randomization and during the whole study:

- All monoamine oxidase (MAO) inhibitors.
- Levodopa and dopa-agonist drugs: apomorphin, ropinirole, pramipexole, rotigotine.
- Reserpine
- Glutamate antagonists: amantadine, memantine, riluzole.
- Anti-arrhythmic drugs inducing bradycardia: diltiazem, verapamil, amiodarone, digitalis, quinidine, sotalol, disopyramide.
- Any other beta blocker antihypertensive medication.
- Central antihypertensive treatments: clonidine, methyldopa, rilmenidine.

#### 5.3.2. Authorized treatments

Patients treated with antihypertensive drugs such as diuretics, angiotensin converting enzyme (ACE) inhibitors, angiotensin receptor blockers (ARBs), or calcium blockers (dihydropyridines only) can continue their treatment at a stable dose during the whole study, with maximum of a dual combination of 2 antihypertensive drugs, and if the patient has stable blood pressure.

Patients treated for depression and stabilized with non IMAO (inhibitors of MAO) antidepressants can continue their treatment at a stable dose during the whole study. Allowed antidepressants drugs are:

- SSRIs (selective serotonin reuptake inhibitors): fluoxetine, paroxetine (see precautions below), citalopram, sertraline.
- SNRIs (serotonin-noradrenaline reuptake inhibitors): duloxetine, venlafaxine.
- TCAs (tricyclic antidepressants): amitriptyline, clomipramine, imipramine, nortriptyline, lofepramine.

Neuroleptics treatment (excluding haloperidol, pimozide, and tiapride, which all have the indication for the treatment of abnormal involuntary movements that occur in HD, such as chorea, in their labeling), if needed to treat a behavior disorder and prescribed for at least 3 months at a stable dose, can be maintained at a stable dose during the whole study, provided that it is approved on a case-by-case basis by the Steering Committee before enrolment of the patient.

Treatments to be used with precautions (because of risk of interactions):

- Alpha-blockers.
- Local beta-blockers (eye drop) or pilocarpine (eye drop).
- Anticholinesterase drugs: donepezil, rivastigmine.
- Strong CYP2D6 inhibitors may increase the blood levels of SOM3355 (such as paroxetine fluoxetine, quinidine, bupropion, dacomitinib, tipranavir).

## **5.4.** CONTRACEPTION

According to the recommendations related to contraception and pregnancy testing in Clinical Trial Facilitation and Coordination Group (CTFG) guidance, based on Calvan® (bevantolol hydrochloride) Summary of Product Characteristics (SmPC) the risk of teratogenicity or fetotoxicity is considered

as possible" in humans taking bevantolol. In consequence, recommendations related to contraception and pregnancy testing in this clinical trial are as following:

Females of child-bearing potential (i.e. fertile, following menarche and until becoming postmenopausal unless permanently sterile) who test negative for pregnancy at screening (pregnancy test) must use a reliable method of birth control during the study and for at least 1 month following the last dose of study drug. A pregnancy test should be also performed at the end of the study (Visit 6).

No contraception measures are needed for male subjects with female partner of childbearing potential.

Highly effective methods of birth control for females include:

- Intrauterine device or intrauterine hormone-releasing system.
- Use of oral, implanted (under the skin), transdermal (patches placed on the skin), or other hormonal methods (shots/injection) of hormonal contraception that stop ovulation. These must have been used for at least 3 months before the Screening Visit.
- Surgery to tie both fallopian tubes female patients who have had both fallopian tubes tied.

If the patient practices true abstinence because of a lifestyle choice (not just to participate in this study), the Investigator may consider an exemption for contraceptive requirements, however, for females a pregnancy test should be done at screening and at the end of the study.

If a female becomes pregnant while receiving the study drug, she should immediately stop taking the medication and notify the Investigator. The patient should attend a final visit to assess her health status. Then, a follow-up with her family doctor / general practitioner should be performed to obtain information about her pregnancy and the birth of her child, including post-natal examination, which will be used to learn more about the effects of the study drug on pregnancy and an unborn baby.

#### 5.5. SCREEN FAILURES

Screen failures are defined as patients who consent to participate in the clinical trial but are not subsequently randomly assigned to the study intervention or entered in the study. A minimal set of screen failure information is required to ensure transparent reporting of screen failure patients, to meet the Consolidated Standards of Reporting Trials (CONSORT) publishing requirements and to respond to queries from regulatory authorities. Minimal information includes demography, screen failure details, eligibility criteria, and any serious adverse event (SAE).

## 5.6. PATIENT IDENTIFICATION AND RANDOMIZATION

Each country will be assigned a 1-digit country code (i.e., 1, 2, 3...). Each participating investigative study center within a country will be assigned a sequential 2-digit number (e.g., 01, 02, 03...), which will be added to the country code to generate the site code or site ID. Each patient will receive a 2-digit number in sequential order at the screening visit after the consent form is signed (e.g., 01, 02,

03...), which will be added to the site code to obtain the patient code or patient ID. Therefore, the Patient IDs will be like 101-01, 101-02, ..., 102-01, 102-02, ..., 201-01, 201-02, ..., 202-01, 202-02....

Enrolled patients who fail screening or discontinue study participation early, regardless of whether treatment was received or not, will retain their patient ID and a new ID will be assigned to the next enrolled patient.

Patients who fulfil all entry criteria will be randomized to receive either SOM3355 at 400 mg/day or 600 mg/day, or placebo, in a 1:1:1 ratio. Randomization will be site-specific and performed by a central Interactive Web Response System (IWRS).

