**Table 4: Estimand of the Primary Analysis** 

Estimand attribute	Primary definition		Rationale (as needed)
Population	Patients with Huntington's disease with choreic movements		
Endpoint	Change from baseline (Visit 0 and Visit 1) to end of maintenance dose (Visit 4 and Visit 5) in TMC score		
Inter-current events	Event	Strategy	Rationale (as needed)
	Receipt of assigned study treatment	Treatment policy	This strategy applied to align the estimand with the application of the ITT principle.
	Prohibited concomitant treatment during the treatment period	While on treatment	This strategy applied up to the time of the prohibited concomitant treatment.
	Discontinuation from study	Hypothetical policy	This strategy applied for randomized and treated patients using a MMRM approach under MAR assumptions.
Summary measure	Difference in adjusted LS means between active arms and placebo from baseline to end of maintenance visit.		

The primary analysis of the primary efficacy endpoint will be based on a mixed-effect linear model for repeated measures (MMRM) to compare each active treatment group to placebo. The model will include the following factors: treatment group, visit, and treatment-by-visit interaction as fixed effects, and baseline TMC score as covariate. An unstructured (US) variance-covariance matrix will be used to model the within-patient errors. If no reliable results under the US assumption can be obtained, the Toeplitz (TP) covariance structure, followed by the autoregressive (AR1) and Compound Symmetry (CS) covariance structure will be used. The Kenward-Roger method will be used to estimate the denominator degree of freedom.

The least square mean (LSM) estimate for each treatment group and difference in LSM estimates at end of maintenance dose between active treatments and placebo group with their confidence intervals will be provided.

To preserve the family-wise error rate at the 0.05 level when comparing the two doses of SOM3355 versus placebo, statistical testing will be carried out using the Holm procedure. The smallest p-value of the two comparisons will be first compared at the two-sided 0.025 level and if statistically significant, the other p-value will be compared at the two-sided 0.05 level.

Sensitivity analyses on the primary efficacy endpoint will be conducted as follows:

- Primary endpoint will be analyzed using the observed cases (no imputations) using an analysis of covariance (ANCOVA) model.

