## 3.6 Subgroup analyses

Subgroup analyses of the primary efficacy (change in Total Maximal Chorea (TMC) score from baseline to the end of maintenance therapy at V5) are planned for the following subgroups:

- patients not taking neuroleptics during the study vs patients taking neuroleptics as concomitant medication during the study
- gender: male, female
- age: < median,  $\ge$  median
- country: France, Spain, UK, Poland, Italy, Germany
- baseline TMC: < median, ≥ median
- baseline TMS: < median, > median

This analysis will be performed on the mITT population, except the neuroleptics subgroup, which will also be repeated on the PP population.

Additional subgroup, correct versus incorrect down titration phase between Visit 5 and Visit 6, is defined as:

- patients who have performed a correct down titration phase i.e. who correctly took the IMP at half dose (1 capsule/ day) for a week and then capsules from placebo bottle for at least 4 days.
- patients who did incorrect down titration
  - o who took 2 capsules/day of IMP so remaining at full dose with no down titration, and then placebo with abrupt IMP discontinuation
  - o or who took the IMP at half dose (1 capsule/ day) for 2 weeks with no placebo wash out or less than 4 days under placebo

For this subgroup, only descriptive statistics on visits for the TMC score will be repeated on the mITT population to show the evolution of the TMC score between V5 and V6 after IMP interruption. In addition, time profiles of the mean TMC scores with standard error of the mean (SEM) will be presented.

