## 4.1.3 Pooling of centres

No pooling of centres will be performed.

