The primary analysis of the primary efficacy endpoint will be based on a mixed-effect linear model for repeated measures (MMRM) to compare each active treatment group to placebo. The model will include the following factors: treatment group, visit, and treatment-by-visit interaction as fixed effects, and baseline TMC score as covariate. An unstructured (UN) variance-covariance matrix will be used to model the within-patient errors. If no reliable results under the UN assumption can be obtained, the Toeplitz (TP) covariance structure, followed by the autoregressive (AR1) and Compound Symmetry (CS) covariance structure will be used. The Kenward-Roger method will be used to estimate the denominator degree of freedom.

The SAS code for the primary analysis is as follows:

PROC MIXED data=dataset method=REML;

CLASS subject treatment visit;

MODEL changeTMC = treatment visit treatment\*visit baselineTMC / ddfm=KR;

REPEATED visit / subject = subject type = UN;

LSMESTIMATE treatment\*visit "TMC change 200 mg vs Placebo" 0 0 -1 0 0 1 0 0 0 / cl elsm;

LSMESTIMATE treatment\*visit "TMC change 300 mg vs Placebo" 0 0 -1 0 0 0 0 0 1/cl elsm:

RUN;

Statistical Analysis Plan	Version 1.0		Page 19 of 37
Sponsor	SOM Biotech	Protocol No	SOMCT03

The least squares mean (LSM) estimate for each treatment group and difference in LSM estimates at end of maintenance dose between active treatments and placebo group with their confidence intervals will be provided. For the lowest p-value 97.5% CI will be provided and for the highest p-value 95% CI will be provided.

To preserve the family-wise error rate at the 0.05 level when comparing the two doses of SOM3355 versus placebo, statistical testing will be carried out using the Holm procedure. The smallest p-value of the two comparisons will be first compared at the two-sided 0.025 level and if statistically significant, the other p-value will be compared at the two-sided 0.05 level.

Descriptive statistics will be presented for the TMC score and changes from baseline by treatment group and by visit (including V6), on imputed data (as described in 4.1.). In addition, time profiles of the mean TMC scores with standard error of the mean (SEM) will be presented.

Sensitivity analyses on the primary efficacy endpoint will be conducted as follows:

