#### Sensitivity #2

Primary endpoint will be analysed using the observed cases (no imputations) using an analysis of covariance (ANCOVA) model including treatment as fixed factor and baseline score as covariate. Results for the outcome of the primary endpoint will be presented for the least square means estimates and 95% CIs. This analysis will be performed on the mITT population.

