## 4.7.2.1 Clinical Global Impression

The CGI-Severity (CGI-S) assessed at baseline is a 7-point Likert Scale that asks the clinicians to rate, considering their total experience with this type of patients, the level of illness due to chorea on the illness severity ranging from normal (1) to extremely ill (7) (CGI-Severity).

Statistical Analysis Plan	Version 1.0		Page 21 of 37
Sponsor	SOM Biotech	Protocol No	SOMCT03

Then, after therapy initiation, the CGI-Change (CGI-C) asks the clinician to assess the overall global change in the choreic symptoms since the start of study drug dosing, in a 7-point Likert Scale ranging from very much worse (7) to very much improved (1).

CGI-S will be assessed at the inclusion (Visit 1 at Day 0), and CGI-C at each following visit (from V2 to V6). For the CGI-C, patients with a score of 1 (very much improved), 2 (much improved) or 3 (minimally improved) will be defined as "Improved" and patients with a score of 4 (No change), 5 (Minimally worse), 6 (Much worse) and 7 (Very much worse) will be defined as "Not improved".

CGI-S (baseline characteristic) and CGI-C results will be analysed descriptively at each visit.

A logistic regression model will be performed for CGI-C at V5 (end of maintenance dose) including the treatment group as the main factor in the model. Estimates along with 95% confidence intervals for the difference in response proportion and the odds ratio of response will be derived from this model.

In addition, histogram will be presented.

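### Patients are randomised by site, but the primary MMRM and the sensitivity #2 ANCOVA omit site and country without a stated reason: valid, yet power may be forgone if TMC change differs materially between sites

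*Protocol*

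**What the plan says.** Protocol 5.6 describes the allocation, at 1:1:1, in one sentence: "Randomization will be site-specific and performed by a central Interactive Web Response System (IWRS". It does not mention strata, block size or balance within site. The synopsis plans 16 to 20 sites.

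For the primary analysis, Protocol 9.4.1 states: "The model will include the following factors: treatment group, visit, and treatment-by-visit interaction as fixed effects, and baseline TMC score as covariate". The SAP 4.7.1 text repeats this, and its code agrees: the class variables are "CLASS subject treatment visit". Sensitivity #2 is an ANCOVA "including treatment as fixed factor and baseline score as covariate".

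Geography enters elsewhere only in ways that leave the treatment comparison unadjusted. SAP 3.6 has a subgroup by "country: France, Spain, UK, Poland, Italy, Germany", SAP 4.1.3 says "No pooling of centres will be performed", and disposition and demographics are tabulated by country and centre. SAP 2.2, which lists departures from the protocol, is silent on site. Neither document says why site is left out of the models.

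**The concern.** When allocation is organised by site, the usual course is either to carry site into the analysis or to explain its absence. Any between-site variance in TMC change that remains after baseline adjustment stays in the error term. Two things could follow: power that adjustment would have recovered is lost, and, if arms are balanced within sites, the model standard error overstates the true variability and the intervals are too wide.

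Site differences are plausible. TMC is a clinician rating made by each site's own staff, and no central rating of it is described, whereas ECGs are read centrally. That shows plausibility only. A stable rating offset at a site largely cancels in a change score, so only site differences in change matter.

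**Working it through.** **1. The plan's own figure.** Inputs from Protocol 9.3 and SAP 1.4: difference 2.5, SD 3.5, 39 per arm, two-sided 0.025, t-test.

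- SE = 3.5 × √(2/39) = 0.793; noncentrality = 2.5/0.793 = 3.154; df = 76.
- Exact power is 80.5% at 39 per arm and 79.4% at 38, so 39 is the smallest n that reaches 80%. The stated figure reproduces without any site term.

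**2. Closed-form guide.** Let ρ be the ICC, the share of the variance in TMC change that lies between sites (assumed). Take perfect balance within site, normal approximation, critical value c = 2.241.

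- Planned model: Φ[(3.154 − c)/√(1−ρ)].
- Site-adjusted model: Φ[3.154/√(1−ρ) − c].
- ρ = 0.05: 82.5% and 84.0%, a gain of 1.5 points.
- ρ = 0.10: 83.2% and 86.1%, a gain of 2.9.
- ρ = 0.20: 84.6% and 90.1%, a gain of 5.5.

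**3. Simulation of the planned MMRM with and without a random site intercept.** There were 2,000 trials per setting, and both models were fitted to the same data.

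- From the documents: 129 randomised, effect −2.5, SD 3.5, two-sided 0.025, UN with Kenward-Roger, and three visit levels (V2, V3, end of maintenance) to match the nine coefficients in the SAP code.
- Assumed: 18 unequal sites (within the planned 16 to 20), 12 random monotone dropouts (leaving 117 = 3 × 39), between-visit correlations 0.6/0.6/0.5, ICC and block size.

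| ICC | Allocation within site | Planned power % | Random site % | Change in points (paired SE) |
|---|---|---|---|---|
| 0 | blocks of 3 | 82.2 | 82.4 | +0.3 (0.1) |
| 0 | unblocked | 81.2 | 81.3 | +0.1 (0.1) |
| 0.05 | blocks of 3 | 82.2 | 83.2 | +1.0 (0.2) |
| 0.05 | unblocked | 82.2 | 82.4 | +0.2 (0.3) |
| 0.10 | blocks of 3 | 81.8 | 84.2 | +2.4 (0.3) |
| 0.10 | blocks of 6 | 80.8 | 83.4 | +2.6 (0.3) |
| 0.10 | unblocked | 81.9 | 83.7 | +1.8 (0.3) |
| 0.20 | blocks of 3 | 83.4 | 89.0 | +5.6 (0.4) |
| 0.20 | unblocked | 81.8 | 86.4 | +4.6 (0.5) |

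Changes are computed before rounding. At ICC 0 there is nothing to recover, so the small plus under blocking is an artefact. If site effects drift over visits (correlation 0.5, blocks of 3), the gains shrink to +1.8 at ICC 0.10 and +3.3 at 0.20.

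**4. Single-endpoint runs** (117 evaluable, 16 and 20 sites, 2,500 trials per setting), change in points:

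| ICC | Blocks of 3 | Unblocked |
|---|---|---|
| 0 | +0.2 to +0.4 | −0.4 to −0.3 |
| 0.05 | +1.0 to +1.3 | 0.0 to +0.5 |
| 0.10 | +2.2 to +2.6 | +1.0 to +1.3 |
| 0.20 | +5.6 to +5.7 | +4.4 to +4.5 |

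A separate check gave about 3 and 4 points at ICC 0.10 and 0.20 with blocks of 3, and about 1 and 4 unblocked.

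**5. Type I error** (MMRM, nominal 2.5%, simulation SE about 0.3), planned/random site at ICC 0, 0.10 and 0.20:

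- Blocks of 3: 2.4/2.5, 1.9/2.4, 1.7/2.8.
- Unblocked: 2.5/2.4, 2.4/2.4, 2.4/2.2.

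**6. Interval width.** Planned model SE against the empirical SD of the estimate:

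- Blocks of 3: 0.786/0.756 = 1.04 at ICC 0.10, and 0.786/0.731 = 1.08 at 0.20.
- Unblocked: 0.783 against 0.788, and 0.784 against 0.784, so there is no excess.

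**7. Alternatives.** Fixed site effects cost 1.4 to 3.3 points at ICC 0 across the single-endpoint runs. Fixed country (MMRM, blocks of 3) costs 0.5 points at ICC 0. At ICC 0.10 it gains 0.8, or 1.8 if half the site variance lies between countries.

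**The case against.** The best defence is that nothing in the plan is wrong. The sample size rests on a total SD of 3.5 and a plain t-test, so the promised power never depended on a site term, and anything recovered is a bonus. The size of that bonus rests on an ICC and a block size that the documents do not give, and the largest gains need an ICC of 0.20. Replacing a primary model fixed in both documents is a large step for a few points. Doing so after an unblinded interim would damage credibility. Convergence was also not tested in SAS.

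Most of this stands. It makes the change optional and governs its timing. It does not remove the point: the omission is unexplained, centre number is already held, and the downside is small.

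Four stronger readings are tempting and are not supported:

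- **The test is invalid or anti-conservative.** The simulated size of the planned test is at or below nominal.
- **The trial is underpowered without site.** The stated power reproduces. 43 less 10% leaves 38.7 per arm, but the claim concerns at least one dose, and that probability is about 91% if both doses have the assumed effect (single-endpoint simulation, ICC 0).
- **Any site difference costs power.** At ICC 0.05 unblocked no gain is demonstrable: +0.2 (SE 0.3) above, and +0.1 (SE 0.2) in a separate 6,000-trial run. In the same run ICC 0.03 gave −0.3 (SE 0.2).
- **The CGI-C, PGI-C and TMC-response models share the problem.** They are logistic models described as "including the treatment group as the main factor in the model". No loss was computed for them, the TMC figures do not carry over, and some 18 site terms would be sparse. They are outside this point.

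**Conclusion.** The point holds as a possible efficiency gain, not as an error. The planned analysis is valid on this matter and N need not change.

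If TMC change differs materially between sites, a random site intercept may recover about 2 to 3 points at ICC 0.10 and about 5 at 0.20 with allocation balanced within site. Without balance, the figures are about 1 to 2 and 4 to 5. At ICC 0.05 the gain is about 1 point with blocks of 3 and not demonstrable when unblocked. Gains are smaller if site effects drift over visits.

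The intervals are too wide (about 4% at ICC 0.10) only if sites differ and arms are also balanced within site. A reader might take site-specific randomisation to mean stratified blocks, but Protocol 5.6 does not say so. ICC, block size and visit correlations are all assumptions, so the actual loss in this trial is unknown and may be nil.

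**What to change.** This is optional and cheap.

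**If the unblinded interim has not been run:**

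- In SAP 4.7.1 add site to the CLASS statement and a random site intercept to the primary MMRM, keeping UN and Kenward-Roger. Add the same intercept to the sensitivity #2 ANCOVA.
- Count a site variance estimated as zero as a valid result, since the model then equals the planned one. In simulation this happened in about 53% of trials at ICC 0 and 5% at ICC 0.10.
- If the model does not converge, replace random site by fixed country and keep UN. Only then turn to the existing rule: "If no reliable results under the UN assumption can be obtained, the Toeplitz (TP) covariance structure", and so on in the planned order.
- Do not use 16 to 20 fixed site effects.
- List the change in SAP 2.2 before the interim, because Protocol 9.4.1 fixes the model without site and SAP 4.12 uses the primary-endpoint method at the interim.

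**If the interim has been run:** keep the planned primary model and add the random-site MMRM as a prespecified sensitivity analysis before database lock. The documents do not say which case applies.

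**Cost:** one SAP paragraph, one entry in SAP 2.2, one class variable, one RANDOM statement and an ordered fallback. No new data are needed. The model is slightly more complex, and power falls by up to about 0.4 points if sites do not differ. If the sponsor prefers to leave the models alone, a sentence saying why site is omitted would close the gap.
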